Quality of life will be measured using the Quality of Life Enjoyment and Satisfaction Questionnaire—Short Form (Q-LES-Q-SF), 52 which measures overall enjoyment and satisfaction with various aspects of life. The 16-item scale is reliable (α =.86) and valid. Participants rate satisfaction with each domain on a Likert scale from 1 to 5.

Exploratory/tertiary outcomes

Sleep will be measured using the Insomnia Severity Index (ISI),⁶⁴ which consists of 7 items evaluating perceived insomnia (e.g., severity, satisfaction with sleep pattern, interference with daily functioning) over the past week. Response options range from 0 (none/not at all) to 4 (very/very much). The ISI has good evidence of reliability and validity in clinical and community samples.⁶⁵ It is responsive to insomnia treatment⁶⁵ and performs well as screening tool for insomnia.⁶⁴

Pain intensity and interference will be measured using the PEG,⁶⁶ which is an ultra-brief, 3-item measure. Participants indicate their pain intensity, pain interference with enjoyment of life, and pain interference with general activity in the past week on a scale from 0 (no pain/does not interfere) to 10 (pain as bad as you can imagine/interferes completely). The PEG has good reliability and validity and is sensitive to change.⁶⁶ This measure will be included because chronic pain is extremely prevalent in the VHA primary care population and is associated with greater psychological distress,⁶⁷ and it may impact treatment engagement or effectiveness.

Behavioral activation/engagement will be measured using the Behavioral Activation for Depression Scale-Short Form (BADS-SF),⁷⁰ which consists of 9 items assessing changes in activation. Participants rate how true each item was for them over the past week on a scale from 0 (not at all) to 6 (completely). The BADS-SF has good reliability and validity. ⁷⁰

Behavioral avoidance will be measured using the Behavioral Avoidance subscale of the Multidimensional Experiential Avoidance Questionnaire (MEAQ),⁷¹ which consists of 11 items assessing overt situational avoidance of unpleasant emotions. Participants rate how much they agree with each item on a scale from 1 (strongly disagree) to 6 (strongly agree).

Healthcare utilization will be assessed using self-report items about non-VA appointments (primary care, emergency department, and mental health visits) at baseline (6 months prior to baseline) and post-assessment (4 months while in study). We will also conduct a chart review in CPRS to obtain objective data (e.g., patient's presenting complaint, diagnoses, GAD-7/PHQ-9 scores, and other indicators of whether appointments were related to anxiety symptoms) from progress notes of VA appointments (primary care, emergency department, and mental health visits) in the 6 months prior to study enrollment, the 4 months in the study, and the 6 months following study completion.

Addition to our assessments in response to the COVID-19 outbreak:

Given the relevance of the COVID-19 outbreak to the study's primary outcome of anxiety, we have included a few questions related to COVID-19 in the baseline, follow-up, and post assessments so that we can understand whether this public health situation had a systematic impact on the study results. The baseline questions assess from March 16, 2020 (when the first case was detected in Onondaga County) to the date of the baseline, and the post questions assess from the baseline to the date of the post. The single item added to the 4, 8, and 12 week assessments references the past week consistent with the other measures given in those assessments. Items added to the acceptability interview will help us understand whether delivery by telehealth modalities impacted treatment engagement (in either condition).

Treatment related outcomes

Treatment satisfaction will be measured by the Client Satisfaction Questionnaire (CSQ), an 8-item self-report questionnaire with evidence of reliability (α = .93) and validity.⁵⁴ Each item rating and the total CSQ score will be used to evaluate participants' satisfaction with the treatment they received.

Treatment credibility will be assessed at post-assessment using a 4-item adapted version⁵⁵ of the Expectancy Rating Scale (ERS),⁵⁶ which asks patients to rate, on a Likert scale from 0 (not at all) to 10 (extremely), how logical this type of anxiety treatment seems, how confident they are that the treatment would eliminate anxiety, how confident they would be in recommending the treatment to a friend with anxiety, and how much improvement they expect to result from it.

Therapeutic alliance will be assessed at post-assessment using the 12-item Working Alliance Inventory-Short Form Revised (WAI-SR),⁸⁵ which asks patients to rate, on a Likert scale from 1 (seldom) to 5 (always), their experience of the therapist in terms of quality of the relationship bond, agreement on the goals of treatment, and agreement on the tasks of treatment. This measure has good reliability and validity.^{85,86}

Acceptability will be assessed by an acceptability interview, which we adapted from our prior work. The semi-structured interview is designed to assess Veterans' satisfaction with and perceived helpfulness of specific components of the intervention (including handouts), or for those who did not attend any intervention sessions, what prevented them from attending and how we could improve the way the treatment is described to appeal more to Veterans. It will be used to identify barriers and facilitators to engagement, adherence, and retention to guide future implementation efforts.

Table 1: Summary of Measures and Time of Administration

Measure	Construct	Telephone	Baseline	Each	Follow-up	Post-
		screening		interventi	assessm	assessm
				on	ent	ent
				session	(telephon	
					e)	
Demographics	Demographics	X	Х			
6-item screener	Cognitive impairment	X				
GAD-7	Anxiety symptom severity	X	Х	Х		X
PHQ-9	Depressive symptom severity	X	X	Х		X
PC-PTSD-5	Probable PTSD (screen)	Х				
Treatment history	Counseling/therapy and	x (past	Х			
	medication use	month)	(lifetime)			
Readiness ruler	Readiness to change		х			
OASIS	Impairment due to anxiety		х		Х	Х
ODSIS	Impairment due to depression		х		Х	Х
DASS-21	Stress / Anxiety / Depression		х		Х	Х
Q-LES-Q-SF	Quality of life		х			Х
ISI	Insomnia		х			Х
BADS-SF	Behavioral activation		х			Х
MEAQ-BA	Behavioral avoidance		х			Х
PEG	Pain intensity/interference		х			Х
Healthcare visits	Healthcare utilization		х			Х
COVID-19	COVID-19 questions		х		Х	Х
CSQ	Treatment satisfaction					Х
ERS	Treatment credibility					Х
WAI-SR	Therapeutic alliance					Х
Interview	Acceptability of intervention					Х

DATA SAFETY, MANAGEMENT, AND SECURITY

All research staff will be trained by the PI in the responsible conduct of research, including privacy, confidentiality, HIPAA and IRB regulations, as well as recruitment procedures, conduct of telephone screening, and data entry, management, and analysis. RAs participate in mandated IRB training as well as internal training on informed consent. Research staff are trained on maintaining confidentiality and the security of the data with supervision by the PI. All study staff are up-to-date with VA Privacy and Information Security and Rules of Behavior training. Only current, IRB-approved research staff will have access to the data; if study staff leave the research team at any point, their access to data will be terminated. All data will be kept strictly confidential and secure per American Psychological Association (APA) ethical standards and IRB requirements.

Research staff conducting eligibility screenings and research assessments will alert the PI to any safety concerns. All research staff are trained by the PI in data collection regarding mental health topics and suicide risk assessment. In addition to the PI, other licensed independent mental health providers will be available as back-up on call clinicians to ensure safety in the event of urgent clinical concerns. For patients receiving the anxiety intervention, session data (i.e. response to PHQ-9 item 9 suicidal ideation question) will be monitored regularly by the PI to ensure patient safety during the treatment. The PI will notify the IRB, in writing, immediately, of all serious and unexpected adverse events, regardless of whether or not the event was related to the study. The PI supervises periodic internal audits to ensure data integrity and management in accordance with VA guidelines and IRB regulations.

Data collection tools such as questionnaires will be labeled with a random identification number, rather than the name, so there will be no way to connect a participant to his/her specific responses without the key. The key with participant names and linked ID numbers will be stored separately from study data to maintain confidentiality and protect participants' privacy.

Data will be used for research purposes only. All data will be stored securely within the VA. No data will be removed from VA premises. Data will be stored in paper (e.g., field notes, questionnaires) and electronic (e.g., data from CPRS) form. Paper data will be stored in locked file cabinets located in locked offices in the Center for Integrated Healthcare's main offices. Electronic data will be stored on the VA secure server in password-protected files. Data obtained through VINCI is stored on secure VA VINCI servers, until it is downloaded by the study team to store on the local secure server. To ensure the protection of Veteran data, VINCI maintains compliance with the guidelines in VA Handbook 1200.12 and all other applicable VA and VHA policies and regulations. Data will not be transmitted outside VA at all. Identifiable data will not be transmitted within VA, with the possible exception of being uploaded to VINCI or sent via encrypted VA email to IRB-approved staff for data analysis. Excel, SAS, SPSS, and Atlas.ti (licenses owned by the Center for Integrated Healthcare and/or accessible through VINCI) may be used for data cleaning and analysis. After data analysis is complete, results from group or aggregate data may be reported in research publications; however, no identifiable data will be included. Data will be maintained as defined in the VHA Records Control Schedule and destroyed at the appropriate time in accordance with these regulations and IRB guidelines.

STATISTICAL ANALYSIS PLAN

The data will be screened for missing cases, outlier scores, and non-normal response distributions. Assumptions underlying statistical models will be assessed by examining standardized residuals, influence diagnostics, and homogeneity of variance (e.g. among groups). Descriptive statistics will be calculated for all variables. Analyses will be conducted using the intention-to-treat approach; participants who are randomized will be analyzed according to their assigned group regardless of amount of treatment received. The a priori alpha level for all analyses is 0.05.

The primary outcome is anxiety symptom severity, measured by GAD-7 scores. The primary analysis will be an analysis of covariance (ANCOVA) controlling for baseline GAD-7 score. Secondary analyses will use the same approach to evaluate effects on other pre-post outcomes (PHQ-9 and Q-LES-Q-SF). We will adjust for baseline scores, thus reducing the residual variance, and theoretically giving us increased power.

Multilevel modeling (MLM) will be used for outcomes with multiple (>2) assessment points (OASIS, ODSIS, DASS-21 subscales). MLM will be used to test the primary null hypothesis that no differences exist in the rate of change in outcomes between the intervention group and PCMHI usual care group against the two-sided alternative that differences do exist. A composite equation consisting of within- and between-person effects will be used to analyze our data. The within-person (level 1) equation estimates participants' unique intercept (time=0) and outcome trajectory. The between-person (level 2) equation estimates the average initial status at time 0 and rate of change in the outcome. Random effects include an intercept and slope. Both level-1 and 2 (subject) residuals are assumed to be normally distributed.

References

- 6. Mendlowicz MV & Stein MB (2000). Quality of life in individuals with anxiety disorders. *American Journal of Psychiatry*, *157*, 669-682.

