Intervention condition: The intervention will be conducted in up to six 30-minute in-person sessions. The first session will occur within two weeks of randomization to minimize potential for changes in health status. Sessions will ideally occur approximately biweekly, but to allow flexibility for Veteran scheduling preferences, may be scheduled anywhere from weekly to monthly. Because the intervention will be modular and Veterancentered, it will be flexible in terms of number of sessions, and this will be determined by the patient and therapist, as in real-world PC-MHI clinical practice. (For the purposes of the research study timeline, if all six sessions are indicated, they will occur as close to biweekly as possible). Participants will be seen in primary care exam rooms to be consistent with routine PC-MHI practice. Requests for telephone sessions will be accommodated (if possible based on module content) after the initial session. During the covid-19 outbreak, telehealth modalities including telephone and VA Video Connect will be used for both initial and follow-up sessions per VA clinical guidance to minimize in-person appointments to reduce unnecessary exposure and risk. At the beginning of each session, participants will complete self-report measures of anxiety and depression for as part of measurement-based care. Participants who endorse >0 on the PHQ-9 item 9 about morbid/suicidal ideation item will be assessed further according to our suicide risk assessment protocol. Therapists will keep track of which modules were completed and in what order on the post-session checklist.

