administration was chosen to improve feasibility and reduce burden on participants. (If a Veteran prefers to complete these assessments in-person, for example if they are coming in to the VA anyway for another appointment, we will accommodate their preference.) These assessments will be brief with only 3 measures (total of 31 items) and will allow us to capture symptoms of anxiety, stress, and depression as well as functional impairment regularly throughout the study period so we can examine how quickly changes occur with treatment. We are interested in the necessary dose to achieve improvement, and these follow-up assessments will permit evaluation of whether changes may occur prior to completing the full intervention (e.g., after only 1-2 vs. 3-4 vs. maximum dose of 6 sessions). In addition, having more regular contact with research staff to complete assessments should help to improve retention in the study over time. These assessments will take approximately 10-15 minutes, and participants will be compensated \$10 for each one they complete.

Post-assessment: At approximately 16 weeks, participants will return for an in-person post-assessment. An RA who is blinded to condition (and was not the interventionist) will administer the self-report measures (see Measures section below and Table 1 for summary). (If necessary or per patient preference, the post-assessment may be conducted via telephone.) After completion of all the aforementioned blinded measures, the RA will open a sealed envelope, which will reveal the participant's condition. The RA will then administer the treatment satisfaction, treatment credibility, and therapeutic alliance self-report measures for all participants who attended at least one treatment session (regardless of condition), and for those in the intervention condition only, the semi-structured acceptability interview. The session will take approximately 90-120 minutes, and participants will be compensated \$50. Participants will also be provided with a resource information sheet and appropriate referrals if interested in obtaining further treatment (e.g., specialty mental health care).

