Process evaluation: As part of our hybrid I effectiveness-implementation trial approach, we will conduct a mixed methods process evaluation⁸¹ of the implementation of the intervention. The goal is to inform future implementation rather than evaluate a specific implementation strategy.⁷⁹ Quantitative data will include acceptability including patient satisfaction and credibility, and feasibility including session attendance. We will also compare patient perception of therapeutic alliance across conditions. Qualitative data will include patient interviews at post-assessment and informal study therapist feedback throughout (e.g., aspects of the intervention or modules that may be challenging to deliver in brief sessions). At the end of the study or whenever a study therapist is leaving the study team, they will be asked to anonymously complete the Study Therapist Debriefing, which includes acceptability, appropriateness, and feasibility⁸⁴ for the VA PC-MHI setting as well as questions implementation barriers and facilitators and training needs.

Intervention Content

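### The week 4, 8 and 12 calls are meant partly to show when change occurs, but the planned slope test, if time is linear, gives only an average rate over 16 weeks

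*Combined protocol and SAP*

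**What the plan says.** The Follow-up assessments paragraph (Method, Procedure) gives three uses for the telephone calls at weeks 4, 8 and 12. One is retention. The other two are scientific: to collect symptoms and impairment regularly "so we can examine how quickly changes occur with treatment", and to evaluate "whether changes may occur prior to completing the full intervention", with 1-2, 3-4 and 6 sessions given as example doses.

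The scales given at these calls are OASIS, ODSIS and DASS-21. The Statistical Analysis Plan assigns them a multilevel model: "MLM will be used to test the primary null hypothesis that no differences exist in the rate of change in outcomes" between the two arms. It adds: "Random effects include an intercept and slope". It names no visit factor, curvature term, contrast at a particular visit, or summary by sessions attended.

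Two other provisions touch the point. The Statistical Analysis Plan opens with a general line, "Descriptive statistics will be calculated for all variables", and a commitment to examine residuals. The Process evaluation paragraph lists "feasibility including session attendance", without linking attendance to outcome.

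On scheduling, the Intervention condition paragraph says of the treatment that "it will be flexible in terms of number of sessions", and that "if all six sessions are indicated, they will occur as close to biweekly as possible".

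**The concern.** The two scientific uses of the calls are questions about timing: at which point improvement appears, and whether it appears before treatment is complete. A straight-line slope summarises five visits in one average rate. Once that is done, the intermediate visits make the rate more precise but no longer say when the change came.

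Two things are at stake. The calls could be made and analysed exactly as planned without the timing question being answered. And a null slope test could be read as showing that patients improve equally quickly in both arms, which it does not show.

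**Working it through.** The plan gives no figure to reproduce here. N=35 is stated without an allocation ratio, standard deviation or target effect.

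**1. What the slope retains.** Inputs: visits at weeks 0, 4, 8, 12 and 16 (protocol) and linear time (inferred). With complete data at common visit times, the mean slope for an arm is the least-squares slope of its visit means: slope = Σ(t − 8)y / Σ(t − 8)². The denominator is 64 + 16 + 0 + 16 + 64 = 160. Take a total improvement of one unit (negative is better):

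| Course | y at weeks 0, 4, 8, 12, 16 | Σ(t − 8)y | Slope per week | True change at week 8 | Fitted change at week 8 (8 × slope) |
|---|---|---|---|---|---|
| All by week 4 | 0, −1, −1, −1, −1 | 4 + 0 − 4 − 8 = −8 | −0.050 | −1 | −0.40 |
| All after week 12 | 0, 0, 0, 0, −1 | −8 | −0.050 | 0 | −0.40 |
| Steady | 0, −0.25, −0.5, −0.75, −1 | 1 + 0 − 3 − 8 = −10 | −0.0625 | −0.5 | −0.50 |

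The earliest and latest courses have the same slope. Whatever the data, a fitted line puts 25%, 50% and 75% of its 16-week change at weeks 4, 8 and 12.

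**2. What a null slope test means.** Assume both arms start to improve at week 1 and reach the same gain G (improvement counted as positive), one in 6 weeks and the other in 14.

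- Fast arm: 0, 0.50, 1, 1, 1 (times G). 16-week slope = 16 × (−2 + 0 + 4 + 8)/160 = 1.00 G.
- Slow arm: 0, 0.21, 0.50, 0.79, 1 (times G). 16-week slope = 16 × (−0.86 + 0 + 3.14 + 8)/160 = 1.03 G.

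The arms are 0.50 G apart at week 8, yet their slopes are practically equal. In simulation (20,000 trials per case, 18 vs 17 patients, complete data, variances as in step 3, G = 0.5 to 1.3 SD) the slope test rejects about 5% of the time, which is its nominal level. If the slow arm gains only half as much, the test points the right way and rejects 8-42% of the time.

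**3. What estimates by visit would deliver.** Assumptions: baseline SD 1, random-intercept variance 0.6, residual variance 0.4, slope variance set so that the baseline-to-week-16 correlation is 0.5 or 0.4, arms of 18 and 17, no dropout.

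- Variance of change at week t = 2 × 0.4 + (t/16)² × v. From 0.6/√(1 + v) = 0.5 or 0.4, v = 0.44 or 1.25.
- At week 8: √(0.8 + 0.11) = 0.95 and √(0.8 + 0.3125) = 1.05.
- Within the intervention arm, 95% half-width = 2.11 × (0.95 to 1.05)/√18 = 0.47 to 0.52 SD.
- Between arms, the multiplier is 2.03 × √(1/18 + 1/17) = 0.688, giving 0.66 to 0.73 SD (from unrounded SDs).

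The same formulas give 0.45-0.47 and 0.51-0.61 SD within the arm at weeks 4 and 12, and about 0.63-0.64 and 0.70-0.84 SD between arms.

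For G = 0.5 to 1.3 SD, the 0.50 G gap in step 2 is 0.25 to 0.65 SD, which lies inside the between-arm half-width throughout.

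**4. Dose.** Suppose the first session falls at week 0-2, with randomization on the baseline day. Biweekly sessions then give 1-2, 3-4 and 5-6 sessions before weeks 4, 8 and 12, so visit roughly tracks the dose bands. Monthly sessions give 1, 2 and 3, so the tracking is only approximate.

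**The case against.** The other side has several good points.

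- **Rate is an ordinary meaning of speed.** The plan does estimate an average rate, and its general descriptive statistics may well include means at each call. A reader might infer that the plan would report nothing on speed. That is too strong. What stands is that nothing commits to change by arm and visit with intervals, and an average rate does not answer whether change precedes completion.
- **Linearity is inferred.** The random-effects sentence could coexist with curved or categorical fixed time. The two extreme courses in step 1 also differ in fitted intercept (−0.4 vs +0.2) and in residual pattern, so the planned residual checks might flag them, though this is uncertain at N=35. The point is therefore conditional on linear time, and the plan names no alternative if the checks fail.
- **Reversal.** A reader might infer that the slope test would favour the slower arm. In step 2 the reversed difference is 0.03 G, effectively zero, and it depends on the arms ending at nearly the same level. The documents give no reason to expect that, and the Study design section asks whether the intervention is superior.
- **The fix cannot rescue the between-arm comparison.** Step 3 bears this out: on average the interval for the week 8 gap would include zero throughout the assumed range.
- **Dose was never promised as a test.** The protocol expresses an interest and says the data will allow the evaluation. A reader might infer that a dose-response analysis was committed to and then omitted, but the wording does not go that far. On the planned schedule, a table by sessions would largely repeat the visit means, in small cells formed by patient and therapist choice.

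**Conclusion.** The point holds as an optional improvement. Under linear time, the planned analysis of OASIS, ODSIS and DASS-21 reports an average rate and cannot show when change occurs, although timing is a stated use of the calls. The equal-slope result is exact arithmetic. The precision figures rest on assumed variances, 1:1 allocation and no dropout.

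The consequence is small. This is a pilot that emphasises feasibility and acceptability, speed and dose are not in the Specific Aims, these scales are not the primary outcome, and the GAD-7 ANCOVA is untouched. The gain lies mainly in describing timing within each arm. Even there a half-width near 0.5 SD means that only early change of about that size would stand clear of zero. Between-arm differences in speed will usually be inconclusive. It would be wrong to conclude that the plan hides a clear difference between arms that a better model would reveal.

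**What to change.** Add a few lines to the Statistical Analysis Plan:

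1. Beside the slope test for OASIS, ODSIS and the DASS-21 subscales, fit the same mixed model with visit (0, 4, 8, 12, 16) as a category by arm. Report within-arm change from baseline and between-arm differences in change at weeks 4, 8 and 12, with 95% confidence intervals.
2. Label these as estimates without significance claims. Five scales at three visits give 15 between-arm estimates.
3. State that a null slope test is not evidence of equal speed.
4. Optionally, tabulate change from baseline by sessions attended before each call, in the intervention arm only. Mark it as purely descriptive, because attendance is decided after randomization.

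No new data are needed: the scales are already collected at these visits, and intervention sessions are recorded in progress notes. The cost is some extra reporting and wide intervals. The slope test and the GAD-7 primary analysis stay as they are.

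### The assessor learns the arm before giving satisfaction, credibility and alliance scales that go to both arms, although only the later interview depends on arm

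*Combined protocol and SAP*

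**What the plan says.** The Post-assessment paragraph (Method, Procedure) sets a fixed order.

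1. The outcome measures are collected blind: "An RA who is blinded to condition (and was not the interventionist) will administer the self-report measures".
2. Once those are complete, the arm is revealed: "the RA will open a sealed envelope".
3. The three treatment-related scales follow: "The RA will then administer the treatment satisfaction, treatment credibility, and therapeutic alliance self-report measures". They are given "for all participants who attended at least one treatment session (regardless of condition").
4. The semi-structured acceptability interview comes last, for the intervention arm only.

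The visit is in person by default, with telephone allowed if needed or preferred. The COVID-19 modifications to the baseline process say that all assessments other than baseline will be done by telephone.

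On use of the data, the Specific Aims make acceptability relative to PC-MHI usual care part of the primary aim, and say that feasibility and acceptability are the pilot's emphasis. The Process evaluation paragraph counts satisfaction and credibility as quantitative acceptability data, and adds: "We will also compare patient perception of therapeutic alliance across conditions". The Statistical Analysis Plan names no analysis for the CSQ, ERS or WAI-SR.

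**The concern.** The protocol values assessor blinding. It specifies a blinded RA at baseline, at the 4-, 8- and 12-week calls and for the main post-assessment measures. It then gives blinding up just before three scales that are administered identically in both arms, and it states no reason for doing so at that point.

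The three scales ask how satisfied participants were, how credible they found the treatment, whether they would recommend it, and how they rate their therapist. Such answers can respond to the tone, pacing or prompting of the person asking. An RA who knows the arm can, without intending to, ask differently in the two arms. That matters most when the items are read aloud. At stake is the credibility of a between-arm reading of acceptability and alliance, which lies close to what the pilot says it is mainly for. Once the data are collected this way, the unblinding cannot be undone.

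**Working it through.** No arithmetic beyond an item count applies. The documents give no power, error rate or planned test for these scales. The check is to ask, for each step of the visit, what the RA must know to carry it out.

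| Step | Who receives it | What the RA must know | What the RA knows under the plan |
|---|---|---|---|
| GAD-7, PHQ-9 and other outcome measures | Everyone | Nothing about treatment | Nothing (blinded) |
| CSQ, ERS, WAI-SR | Attenders of at least one session, both arms | Attendance, yes or no | Arm |
| Acceptability interview | Intervention arm | Arm | Arm |

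The second row is the only mismatch.

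**How much is affected.** The Measures section gives 8 items for the CSQ, 4 for the ERS and 12 for the WAI-SR: 8 + 4 + 12 = 24 items, all collected after the envelope is opened.

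**Is the comparison between arms real?** For alliance, yes: the Process evaluation paragraph states it. For satisfaction and credibility it is inferred from two facts: acceptability is to be evaluated against usual care (Specific Aims), and both scales are given in both arms. The interview cannot supply the comparison because only one arm receives it.

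**Could the RA's knowledge matter?** By telephone, the RA would ordinarily read the items out. Telephone is an option in the Post-assessment paragraph and the stated mode under the COVID-19 modifications, so spoken administration may be common.

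**Would reordering break anything?** The content, recipients and number of items stay the same. The envelope is still opened, one step later. The interview includes questions for people who attended no intervention session (Measures, Acceptability), so the envelope must still be opened for non-attenders. The new order allows this.

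**The case against.** The strongest reply is that the change buys little. The scales are self-report, and participants know who treated them. Questions about that treatment and therapist invite remarks that disclose the arm even with the envelope shut. In-person administration is the written default, and the outcomes that carry the effectiveness question are already finished under blinding. All of this stands. It limits the benefit to removing the RA's certain, advance knowledge of arm, and it keeps the severity modest. It does not supply a reason for the present order.

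A second reply is that the RA may need the arm to say which treatment the items refer to. The protocol does not say so, and neutral wording about the appointments attended during the study would serve in both arms.

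Three stronger readings are tempting and should not be drawn.

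- **That attender-only scales contradict the SAP.** The SAP says "Analyses will be conducted using the intention-to-treat approach", meaning analysis by assigned group whatever treatment was received. Attenders can still be analysed by assigned group, and someone with no session has no treatment or therapist to rate. There is no contradiction.
- **That the bias favours the intervention, or inflates the false-positive rate by a calculable amount.** Nothing in the documents fixes a direction, since a wish to please could raise ratings in both arms. Any error rate would rest on an invented bias, an assumed split of the 35 participants and a test that the SAP does not specify.
- **That the primary outcome is compromised.** It is not, because the GAD-7 is completed before the envelope is opened.

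**Conclusion.** The point holds in a limited form. The RA is unblinded one step too early, so all 24 items of the CSQ, ERS and WAI-SR are gathered by someone who knows the arm and does not need to. The consequence is an avoidable opening for interviewer influence on the stated alliance comparison, and on the satisfaction and credibility data behind the comparative acceptability aim. Its size and direction are unknown.

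The conclusion rests on two readings of the text: that the visit runs in the order written, and that the RA administers the scales, in some cases by voice. If participants complete them on paper without the RA's involvement, the risk is smaller. Participants remain unblinded either way. This is a cheap improvement of modest severity, and it does not touch the effectiveness analyses.

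**What to change.** In the Post-assessment paragraph, reverse the two steps:

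1. After the blinded outcome measures, give the CSQ, ERS and WAI-SR to every participant with at least one session. The RA works from a yes/no attendance flag prepared by someone else, which does not show the arm, and uses wording that does not name the condition.
2. Then open the envelope, for attenders and non-attenders alike, to determine who receives the intervention-only interview.

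While editing, reconcile one related passage. The COVID-19 addition to the Measures section says that the new interview items will inform about engagement in both conditions, whereas the Post-assessment paragraph restricts the interview to the intervention arm.

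The cost is a reordered visit script and one attendance flag per participant. A participant may still reveal the arm while answering, but that is already possible, and the main outcomes will have been recorded by then. The sample size, the measures and the other analyses are unchanged.
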